4.9.4.5 Optional Measures

Exploratory measures including the Insomnia Sleep Index (ISI), cough counting, mucin concentrations (MUC5AC, MUC5B) from induced sputum samples, and EXACT-Pro were included in the protocol as optional measures. Insufficient data are available for these tests to warrant analysis of these data; thus, no data will be summarized for these measures.

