3.2.3 Other Endpoints

Other, tertiary and exploratory endpoints will also be assessed including changes from baseline to follow-up in;

- Responder rates utilizing established clinically meaningful thresholds for SGRQ (4 points)¹⁷ and CAT (2 points)¹⁶
- Change in other QOL measures including CASA-Q and EXACT-PRO
- Change in lung function as measured by FEV₁ and FVC
- Change in sleep patterns as assessed by the Insomnia Sleep Index (ISI)
- Change in cough count as assessed by a cough counting monitor
- Mucin concentrations (MUC5AC, MUC5B) from induced sputum samples
- Quantitative High Resolution CT Scan (HRCT) metrics including airway volume, total airway count, and lobar volumes
- Device performance

In addition to the endpoints described above, additional safety analyses in support of the primary study outcome and to assess the totality of safety profile of the RheOx Bronchial Rheoplasty, will be conducted.

Adverse events reported from the day of the index procedure through completion or termination of the study will be assessed. AEs and SAEs will be summarized using a standard medical coding dictionary (MedDRA). AEs and SAEs will be also analyzed by severity, relatedness to the device and/or procedure and within discrete time periods relative to the index procedure.

COPD exacerbations will also be analyzed by severity (mild, moderate, and severe) based on commonly accepted clinical definitions as defined in GOLD 2018 Report¹⁸.

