7.2 Description of Visits

7.2.1 Visit #1. Screening and Enrollment

Subjects who meet the eligibility criteria and have signed an informed consent form may be enrolled in the study. Assessments performed exclusively to determine eligibility for this study will be done only after obtaining signed informed consent from the subject. Assessment performed for clinical indications (i.e., not exclusively to determine study eligibility) may be used for screening evaluation even if the studies were completed before informed consent was obtained.

All screening procedures must be completed within 90 days prior to start of study treatment.

Note: If the subject experiences a COPD exacerbation or other change in functional status between screening and the first bronchoscopy, screening procedures should be repeated as appropriate at the investigator's discretion. Refer to the Table 7.1 Schedule of Events for listing of required screening procedures.

General Screening Notes:

High Resolution CT Scan

High resolution computed tomography (HRCT) is incorporated as a tool to define subject inclusion criteria and to assess post treatment changes. CT acquisition will be per the CT Core Manual provided separately to each site upon completion of training by the designated CT core lab for this study.

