7.2.7 Visits #7 In-office Follow-up Visit (3 months post Bronchoscopy # 2)

Subjects will return for follow-up visits at 3 months \pm 2 weeks after Bronchoscopy #2 (Visit 4). Refer to the Schedule of Events table for a complete listing of required tests.

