7.4 Schedule of Events (Table 7.1)

Table 7.1: Schedule of Events

	Visit #1: Screening	Visit #2: Bronchoscopy #1	Visit #3: Follow-up 1 week Post-Bronchoscopy #1	Visit #4: Bronchoscopy #2	Visit #5: Follow-up 1 week Post-Bronchoscopy #2	Visit #6: Follow-up 1 month Post-Bronchoscopy #2	Visit #7: Follow-up 3 month Post-Bronchoscopy #2	Visit #8: Follow-up 6 month Post-Bronchoscopy #2	Visit #9: Follow-up Phone Call 10 month Post-Bronchoscopy #2	Visit #10-14: Annual Follow-up 1 - 5 years Post-Bronchoscopy #2
Window			± 3 days	-3 to +6 weeks	± 3 days	± 7 days	± 2 weeks	± 4 weeks	± 2 weeks	± 4 weeks
Informed Consent	X									
Inclusion/Exclusion Criteria	X									
Medical History	X									
Exacerbations History	X	X	X	X	X	X	X	X	X	X
Concomitant Meds	X	X	X	X	X	X	X	X	X	X
Adverse Events		X	X	X	X	X	X	X	X	X
Physical Exam	X	X ¹	X	X ¹	X	X	X	X		X
CBC & Blood Panel	X	X ¹		X ¹			X	X		X
Cotinine Test	X									
EKG	X	X ⁴		X ⁴			X	X		X
Spirometry	X			X ¹			X	X		X
DLCO/Body Pleth	X			X ¹			X	X		X
Six Minute Walk Test	X									
CT Scan	X			X ¹				X		
Bronchoscopy		X		X						
Bronchoalveolar lavage		X		X						
RheOx Bronchial Rheoplasty		X		X						
Induced Sputum Sample	X						X	X		X
SGRQ	X			X ¹			X	X		X
CAT Score	X			X ¹			X	X		X
CASA-Q	X			X ¹			X	X		X
ISI ⁵	X			X ¹			X	X		X
Cough Counting Monitor ⁶	X						X	X		X ⁷
EXACT-PRO ⁸	X	DAILY								
Note 1:	Noted activities are completed prior to bronchoscopy.									
Note 2:	Adverse Events are noted before and after bronchoscopy.									
Note 3:	Overnight Hospital Stay at discretion of PI									
Note 4:	An EKG is recorded prior to the initiation of RheOx procedure and during at least one energy delivery; anesthesia EKG may be used.									
Note 5:	Subjects with clinically significant insomnia at baseline as defined by a ISI score of ≥ 8 points ²¹ , may be asked to complete optional polysomnography testing at baseline and 3-months follow-up.									
Note 6:	In this study, VitaloJAK cough monitor is an exploratory outcome measure. Patients willing to participate are encouraged to wear the 24 hour cough monitor at the 4 visits specified, but it is not mandatory.									
Note 7:	12-month visit only									
Note 8:	In this study, EXACT-PRO is an exploratory outcome measure to quantify and measure exacerbations of COPD. Patients are encouraged to complete the questionnaire daily during the first year (up to Visit #10), but it is not mandatory. Daily patient compliance will not be a reason for removal from the study.									

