8.4 Outcome Analysis

Descriptive statistics will be utilized to summarize and report on data for all subject and outcome variables. Categorical data (e.g., age, gender) will be reported in frequency distributions. Certain dichotomous data (e.g., subjects with Serious Adverse Events) will also be presented as rates. Continuous data (e.g., age, FEV₁) will be summarized using mean, standard deviations, medians, minimums, maximums, and interquartile ranges. Additional subgroup and other multivariable analyses may be performed including examination of the association between subject risk factors (e.g., age, gender) and trial outcomes, and the potential contributions of these factors.

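### SAP 4.9.4.5 reports nothing for four prespecified exploratory measures, using an optional label the protocol does not support for ISI or state for induced sputum, and giving no counts

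*SAP*

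**What the plan says.** Protocol 3.2.3 lists eight exploratory endpoint bullets. Three are ISI, cough count and "Mucin concentrations (MUC5AC, MUC5B) from induced sputum samples". EXACT-PRO shares a fourth bullet with CASA-Q. SAP 3.2.3 repeats the list and calls the measures prespecified.

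SAP 4.9.4.5 then says of all four that they "were included in the protocol as optional measures", and: "Insufficient data are available for these tests to warrant analysis of these data; thus, no data will be summarized for these measures".

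Protocol 8.4 says: "Descriptive statistics will be utilized to summarize and report on data for all subject and outcome variables". The synopsis makes the same commitment.

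Protocol 7.2.1 says of the screening visit: "Refer to the Table 7.1 Schedule of Events for listing of required screening procedures". Protocol 7.2.7 says of the 3-month visit: "Refer to the Schedule of Events table for a complete listing of required tests". Sections 7.2.8 and 7.2.10 use the same wording for the 6-month and annual visits. The notes to Table 7.1 say:

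- Note 5 (ISI): patients with an ISI score of at least 8 at baseline "may be asked to complete optional polysomnography testing at baseline and 3-months follow-up".
- Note 6 (cough monitor): "Patients willing to participate are encouraged to wear the 24 hour cough monitor at the 4 visits specified, but it is not mandatory".
- Note 8 (EXACT-PRO): daily completion in the first year is encouraged but not mandatory.
- Induced sputum: no note.

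**The concern.** The SAP gives two grounds for reporting nothing. The first, that the protocol made these measures optional, can be checked and does not fit all four. The second, too little data, cannot be checked because no count or threshold accompanies it.

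Protocol 2.4 says the device is intended to reduce mucus production and cough, and protocol 8.1 says the study is unblinded. Mucin concentration is a laboratory measure that bears on mucus and does not depend on patient report. A reader of the study report would be told that the protocol made it optional and that data were too few, with no means of judging either statement. SAP 1 requires departures from the SAP to be explained in the study report. This omission is written into the SAP, so that rule does not reach it.

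**Working it through.** The plan states no figure to reproduce. The check sets passages side by side and counts.

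**1. The optional label against the protocol**

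| Measure | Scheduled in Table 7.1 | Note | Label supported? |
|---|---|---|---|
| Cough count | screening, 3, 6, 12 months | 6: voluntary | Yes |
| EXACT-PRO | daily to Visit 10 | 8: voluntary | Yes |
| ISI | screening, Visit 4, 3 and 6 months, annually | 5: only polysomnography optional | No |
| Induced sputum (mucin) | screening, 3 and 6 months, annually | none | Not stated anywhere |

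A mark in Table 7.1 does not by itself make a test mandatory, because the two voluntary measures stand in the same table. What separates them is that each carries a note saying so. For ISI the note is specific and attaches the option to something else. For sputum the conclusion is drawn from silence.

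**2. Size of the omission**

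- Protocol 3.2.3 bullets with no output: ISI, cough count, mucin = 3 of 8, plus EXACT-PRO from a fourth.
- Measures whose optional label lacks support: 2 of 4 (ISI firmly, sputum by inference).

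**3. Whether any planned output shows how much data exists**

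- Tables: 14.1.1 to 14.1.5 (5) + 14.2.1 to 14.2.9 (9) + 14.3.1 to 14.3.8 (8) = 22. Listings: 16.2.1 to 16.2.4 = 4. None names any of the four measures.
- Table 14.1.2 has 10 rows, all visits. It does not count tests.
- The quality-of-life shells (14.2.4 and 14.2.5) name CAT, SGRQ and CASA-Q only.
- SAP 5.2 tabulates follow-up compliance through SAP 4.3, which covers disposition. It also says that all available data are used, and it sets no minimum number.

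**4. Scheduled assessments, as ceilings only**

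These assume 30 treated patients and full follow-up.

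- ISI: Visits 1, 4, 7, 8 and 10 to 14 = 9 per patient; 9 × 30 = 270. Through 12 months: 5 per patient. If Bronchoscopy #2 is not done, Visit 4 falls away, leaving 8 and 4.
- Induced sputum: Visits 1, 7, 8 and 10 to 14 = 8 per patient; 8 × 30 = 240. Through 12 months: 4 per patient.

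The ISI ceiling is lower in practice for patients enrolled before the April 2019 revision added it. The number obtained is not stated and cannot be estimated from the documents.

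**5. Protocol 8.4**

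All four measures stand under protocol 3.2, Outcome Measures, so the 8.4 commitment covers them. Few values limit precision, but they do not prevent a count, a median or a listing.

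**The case against.** The strongest reply is that the omission is disclosed, concerns exploratory endpoints in an unpowered study of at most 30 patients, and appears in a plan that says its analyses were defined before database lock. That stands. It limits the weight of the point without supplying the missing count or the missing support for the label.

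Four further replies have force:

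- **The deviation outputs.** A reader might infer that completeness cannot be traced at all. SAP 4.4 gives a test not completed per protocol as an example of a minor deviation, and Table 14.1.4 and Listing 16.2.2 report deviations. If ISI and sputum were treated as required, missed tests could appear there by patient and visit. This is indirect: it does not count results obtained, covers neither the voluntary measures nor assays, and may not work for a test that was treated as optional.
- **Sputum.** A reader might infer that the protocol plainly required mucin measurement. It schedules a sample but describes no assay schedule. Site training in sputum collection (protocol 4.2) does not settle the matter, since voluntary procedures also need training. The supportable statement is that neither document contains a passage making sputum optional in the protocol, apart from the SAP's own label.
- **Remaining evidence.** A reader might infer that only patient report is left. That is not so: SAP 4.9.4.3 and 4.9.4.4 keep lung function and quantitative HRCT. Neither measures mucin, but both are non-questionnaire measures.
- **EXACT-PRO.** It is a voluntary daily diary, so an expected number per visit has no meaning, and the SAP contains no scoring derivation. The fix allows for this.

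**Conclusion.** The point holds as a reporting defect. The optional label is right for cough counting and EXACT-PRO, unsupported for ISI, and not stated in the protocol for induced sputum. The insufficiency ground has no count or criterion behind it, and reporting nothing departs from protocol 8.4. The extent is three of eight exploratory bullets and part of a fourth. The primary safety analysis and the secondary SGRQ, CAT and hospitalization analyses do not change. The plan should be amended, but the study's main conclusions do not depend on it.

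A reader might infer that the measures were dropped because of what they showed. Nothing in the documents supports that. They do not say how much data exists, or whether sputum was collected or assayed. The later addition of ISI and cough count could explain sparse baseline values, although the SAP does not give this reason and it would not make ISI optional.

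The conclusion on sputum assumes that an unmarked row, in a table that marks its voluntary measures, was not meant as voluntary. A manual outside these two documents could say otherwise.

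**What to change.** In SAP 4.9.4.5:

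1. Remove the optional label for ISI and induced sputum/mucin. Keep it for cough counting and EXACT-PRO, citing Notes 6 and 8 of Table 7.1.
2. Add one count table with the number of patients who have a baseline value and a follow-up value, by visit, for ISI, mucin and cough count. For mucin, count samples collected and samples assayed separately. Give an expected number only for ISI (from the amendment that added it) and for sputum.
3. For EXACT-PRO, report the number of patients who contributed diary data and the number of diary days, with no expected number per visit.
4. Replace the statement that nothing will be summarized with a descriptive summary or patient listing of the ISI, mucin and cough-count values held, without hypothesis tests and marked as imprecise.
5. Record any measure still not reported, including EXACT-PRO if it is not scored, in the clinical study report with its reason, as a departure from protocol 3.2.3 and 8.4.

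The cost is SAP wording, one count table and a few short listings, some possibly empty. No new data collection is needed.

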5 GENERAL INFORMATION

5.1 Statistical Software

The creation of analysis datasets and all statistical analyses will be performed using SAS[®] version 9.4 or higher.

CONFIDENTIAL:

This document and its contents are the property of Gala Therapeutics, Inc. Any use, reproduction or distribution without the written permission of Gala Therapeutics, Inc. is prohibited.

	TYPE: Clinical Trial Document	Document No:	CLN-0000X
	TITLE: CS003 Statistical Analysis Plan	Revision:	A
		Release Date:	
		DCN	Page 12 of 44

5.2 Handling of Missing Data

Patient compliance with required follow up will be tabulated and reported as described in section 4.3. All analyses (tables and figures) will be conducted using all available data. No imputation or other evaluation of missing data will be performed.

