A total of 47 bronchoscopies were completed where the Gala therapy was administered; 25 in the right side airways and 22 in the left side airways. The average age of the treatment patients was 66.3 years, ranging from 53 to 78, with a median 40 pack years smoking and FEV₁ % predicted of 59 with a range of 30 to over 90%. The patients averaged 428 meters on the six-minute walk test (6MWT) at screening. Despite the high 6MWT, the subjects still had severe symptoms of cough and mucus hypersecretion yet the impact on exercise performance was less pronounced, which may be indicative of this patient population.

Data reported as of May 3, 2018 supports a favorable safety profile with no device-related serious adverse events. There were no reported cases of sustained cardiac arrhythmias during or after the procedure. The data also supports favorable clinical utility with an average CAT score improvement of approximately 8 points at 3 and 6 months post-treatment. For reference, the Minimally Clinically Important Difference (MCID) is a reduction of 2 points. Similarly, the average SGRQ score improved by nearly 20 points at 3 and 6-months post-treatment. For reference, the MCID is a reduction of 4 points. Based on these results further clinical study is warranted.

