7.5 Removal of Subjects

Subjects may be taken off the study treatment and/or removed from the study at any time at their own request. Subjects may also be withdrawn at the discretion of the investigator for safety, behavioral (e.g., subject not compliant with study treatment for more than two continuous weeks) or administrative reasons.

The reason(s) for discontinuation will be documented on the End of Study eCRF.

Reasons for withdrawal may include:

- Patient voluntarily withdraws from treatment (follow-up permitted);
- Patient withdraws consent (termination of treatment and follow-up);
- Patient is unable to comply with protocol requirements;
- Patient experiences adverse reaction that makes continuation in the protocol unsafe;
- Investigator determines continuation on the study would not be in the patient's best interest;
- Patient becomes pregnant during treatment period;
- Patient is lost to follow-up.

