8.3 Evaluable Cohort

All subjects who have entered the treatment room for Visit #2 will be included in the safety endpoint analysis (Safety Population). Subjects who have received at least one treatment will be included in the evaluable cohort for clinical utility.

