4.9.1 St. George's Respiratory Questionnaire (SGRQ)

SGRQ total score and changes from baseline will be summarized by scheduled time point using descriptive statistics. The mean, standard deviation (SD), median, and inter-quartile range (IQR) will be reported. Statistical testing to evaluate change from baseline using methods consistent with the statistical assumptions required to support the analyses may also be conducted for exploratory purposes. P-values from a Sign test corresponding to non-parametric approach to test whether the median differs from zero and confidence intervals will be reported.

CONFIDENTIAL:

This document and its contents are the property of Gala Therapeutics, Inc. Any use, reproduction or distribution without the written permission of Gala Therapeutics, Inc. is prohibited.

	TYPE: Clinical Trial Document	Document No:	CLN-0000X
	TITLE: CS003 Statistical Analysis Plan	Revision:	A
		Release Date:	
		DCN	Page 10 of 44

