4.9.2 COPD Assessment Test (CAT)

CAT total score and changes from baseline will be summarized by scheduled time point using descriptive statistics. The mean, SD, median, and IQR will be reported. Statistical testing to evaluate change from baseline using methods consistent with the statistical assumptions required to support the analyses may also be conducted for exploratory purposes. P-values from a Sign test corresponding to non-parametric approach to test whether the median differs from zero and confidence intervals will be reported.

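### SGRQ and CAT change is summarised only in patients with a score at each visit, and the SAP bars any evaluation of missing scores; benefit may be overstated, with no way to bound it

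*SAP*

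**What the plan says.** Protocol 8.3 defines the cohort: "Subjects who have received at least one treatment will be included in the evaluable cohort for clinical utility". SAP 4.2.1 defines its Evaluable Population in the same way and bases all analyses on it.

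Change from baseline in SGRQ and CAT at 6 and 12 months makes up two of the three clinical-utility endpoints (SAP 3.2.2). SAP 4.9.1 states: "SGRQ total score and changes from baseline will be summarized by scheduled time point using descriptive statistics". SAP 4.9.2 says the same for CAT. Both sections add exploratory testing: "P-values from a Sign test corresponding to non-parametric approach to test whether the median differs from zero and confidence intervals will be reported". No longitudinal model is planned.

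SAP 5.2 governs missing scores: "All analyses (tables and figures) will be conducted using all available data. No imputation or other evaluation of missing data will be performed".

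Protocol 7.5 lists reasons for withdrawal that can be related to outcome, among them "Patient experiences adverse reaction that makes continuation in the protocol unsafe" and investigator judgement. SAP Table 14.1.1 counts exits for death and for AE/SAE, and Table 14.1.2 counts death as a visit not completed. None of this feeds into the SGRQ or CAT summaries.

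**The concern.** The cohort is everyone treated, but the 12-month figure describes only those who survived, stayed in the study and returned a score. The two groups have the same mean change only if the missing patients did as well as the others. There is no control arm in which similar losses might partly cancel. A patient's 3- and 6-month scores count at those visits but do not inform the 12-month estimate when the 12-month score is absent.

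The same problem affects the long-term columns. Table 14.2.5 gives each year's change from baseline in whoever attended that year. A steady mean from year 2 to year 5 could mean that the effect lasts, or that patients who did poorly have left. The table gives no 12-month value for the same patients, so the reader cannot tell which.

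What is at stake is the reading of clinical utility, not a confirmatory test: the study is unpowered and safety is primary.

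**Working it through.** The documents give no dropout rate, SD of change or assumed effect, so there is no planned figure to reproduce. Missing shares and SD below are assumptions.

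**Inputs from the documents.** N is at most 30 (SAP 4.1). For scale, Protocol 1.3 reports that in the first-in-human (FIH) study "the average SGRQ score improved by nearly 20 points at 3 and 6-months post-treatment", and that CAT improved by about 8. The responder thresholds are 4 points for SGRQ and 2 for CAT (SAP 3.2.3).

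**Step 1: bound.** With k of N scores missing, mean benefit B_obs in observed patients and B_mis in missing patients:

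overstatement = (k/N) × (B_obs − B_mis)

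For SGRQ with B_obs = 20, k = 6 and B_mis = 0: (6/30) × 20 = 4.0 points. The all-treated mean is then 16, and the reported 20 is 25% too large. For CAT: (6/30) × 8 = 1.6 points.

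| Missing patients' benefit | SGRQ: 3, 6, 9 of 30 missing | CAT: 3, 6, 9 of 30 missing |
|---|---|---|
| Same as observed | 0, 0, 0 | 0, 0, 0 |
| Half | 1.0, 2.0, 3.0 | 0.4, 0.8, 1.2 |
| None | 2.0, 4.0, 6.0 | 0.8, 1.6, 2.4 |
| Worse than baseline by the threshold | 2.4, 4.8, 7.2 | 1.0, 2.0, 3.0 |

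With 1 of 30 missing, the worst row gives (1/30) × 24 = 0.8 SGRQ points.

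**Step 2: dropout driven by an observed score.** Simulation with n = 30, change at Visit 4, 3, 6 and 12 months, assumed SD 15, between-visit correlation 0.5 or 0.7, and dropout before 12 months depending on the 6-month change (log-odds slope 1 or 2 per SD), 3,000 runs per cell. With a true change of −20, the available-case 12-month mean is too favourable by about 3–8%, 6–14% and 9–20% at 10%, 20% and 30% missing. In points that is 0.03 × 20 = 0.6 up to 0.20 × 20 = 4.0. With a true change of −8 the points are about the same, because dropout depends only on the deviation from the mean, but the percentages are larger: about 7–19%, 17–33% and 24–52%. A likelihood estimate that uses the earlier scores stays within about 3% of the truth, with a standard error similar or at worst roughly 10% larger.

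**Step 3: what the model does not repair.** Two-visit simulation, n = 30, SD 15, correlation 0.7, about 20% dropout, true 12-month change −12.0:

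| Dropout depends on | Available-case mean | Model using 6-month score |
|---|---|---|
| Nothing (random) | −11.95 | −11.95 |
| 6-month score | −13.86 | −11.97 |
| Unseen 12-month score | −14.70 | −13.45 |

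In the last row the bias falls from 14.70 − 12.0 = 2.7 points to 13.45 − 12.0 = 1.45 points, so about half remains.

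**Step 4: the Sign test.** In the Step 2 design with a true −20, the available-case p-value was larger than the full-data p-value in 43–87% of runs, and in more than half the runs in 11 of 12 cells, because n falls. With a true −8 the result is mixed: rejection at 0.05 fell from 0.60 to 0.56 in some slope-1 cells and rose from 0.59 to 0.79 in the strongest.

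**The case against.** The strongest reply is that the direction is not shown. The documents say nothing about how many scores will be missing or how leavers fared, and the bias is zero if leavers benefited equally. That stands. A reader might infer that the reported benefit is biased upward as a matter of fact; the documents support only that it may be.

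Four other readings also go too far:

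- That the p-value moves towards benefit. Step 4 shows that it need not.
- That earlier scores are discarded. They count in the earlier columns of Table 14.2.4, and Table 14.2.5 does report change from each attending patient's own baseline. Only the comparison with 12 months is absent.
- That a patient who stops treatment is lost. Protocol 7.5 permits follow-up after withdrawal from treatment, and the notes to the Schedule of Events continue follow-up to 5 years when the second bronchoscopy is not done. Only death, study exit or a missed score removes a patient.
- That durability to 5 years is a secondary endpoint. The endpoint is set at 6 and 12 months.

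The plan is also not silent on losses. SAP 4.3 lists withdrawal reasons and last participation dates, SAP 5.2 has follow-up compliance tabulated, the tables show N per visit, and death is in the primary safety analysis. A reader can therefore see how many are missing and often why, but not what that does to the mean.

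Finally, a repeated-measures model may look heavy for an unpowered feasibility study, and Step 2 uses the dropout pattern that suits it. Both are fair. They argue for a supportive analysis with a simple fallback, accompanied by a sensitivity estimate. They do not justify barring evaluation altogether, since means, 95% intervals and p-values will be printed.

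**Conclusion.** The point holds in conditional form. SAP 5.2 confines the SGRQ and CAT change analyses to patients with a score at each visit and rules out any evaluation of the rest, while the stated cohort is everyone treated. If patients without scores did worse, the 6- and 12-month mean benefit is overstated, and nothing planned would detect or bound it.

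On the SGRQ scale the overstatement runs from zero, through roughly 0.6 to 4 points when 10–30% are missing through dropout on the 6-month score, to 6 points if 9 of 30 are missing with no benefit. These figures rest on assumed missingness, an assumed SD of 15 for the simulation and the FIH benefit for the bound. With few scores missing the effect is minor; with none it vanishes. The later columns of Table 14.2.5 cannot by themselves support a claim of lasting effect.

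**What to change.** 1. In SAP 5.2, in the sentence "No imputation or other evaluation of missing data will be performed", strike the part that bars other evaluation.
2. In SAP 4.9.1 and 4.9.2, keep the observed-case summaries and add two supportive analyses:
   - (a) A repeated-measures estimate of mean change with 95% CI at 6 and 12 months in all treated patients, using baseline score and every post-baseline visit through 12 months, with a simple covariance structure named as fallback because n is at most 30.
   - (b) A sensitivity estimate that gives zero change to treated patients who died, or who exited the study for an AE or by investigator decision.
3. In Table 14.2.5, show beside each 2- to 5-year column the 12-month change in the same patients.

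The cost is SAP wording, one standard SAS model per questionnaire and a few table rows, with no new data or patients. The downsides are that (a) assumes missingness at random given earlier scores, so some bias remains if dropout depends on unseen scores, and that the reported benefit may come out smaller. The change should be made before database lock, since SAP section 1 classes analyses designed after lock or freeze as post hoc.
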